9 SELECTION OF PATIENTS

9.1 SAMPLE SIZE

It is planned to recruit 141 patients (47 patients per arm), in 2 centers in Egypt.

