10 TREATMENT OF TRIAL PARTICIPANTS

10.1 RANDOMIZATION

Before randomization, fulfillment of the inclusion/exclusion criteria should be assured and the signed informed consent obtained. After that, eligible patients will be randomized in a 1:1:1 allocation ratio, into one of the three treatment groups, to receive either placebo or one of the two doses of Heptex. Randomization will be done using interactive response technology.

Control Arm 1:

Placebo (Rice bran) in 2 capsules size 1, administered PO TID on empty stomach with plenty of water.

Experimental Arm 2:

The contents of one capsule of Heptex is equally distributed and inserted into 2 capsules size 1, administered PO TID on empty stomach with plenty of water.

Experimental Arm 3:

The contents of two capsules of Heptex is equally distributed and inserted into 2 capsules size 1, administered PO TID on empty stomach with plenty of water.

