16 STATISTICAL CONSIDERATIONS

16.1 SAMPLE SIZE CALCULATION⁶

Reference to Sanyal AJ, et al. There was a decrease in Alanine aminotransferase level among placebo arm of -20 (U/liter) among the placebo arm while for the active arm, a double of this improvement will be of clinical value. Accordingly, with an alpha error of 5% using one-sided 95% CI of Mann–Whitney U test, a sample power of 80% and an effect size between placebo and lowest active dose of 0.63, a sample of 43 patients for each arm will be required plus an expected drop-out rate of 10% during 9 months' study duration. Thus, a sample of 47 patients per each treatment arm will be appropriate and the total same of the 3 arms will be 141 patients.

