16.3 STUDY ENDPOINTS

During interim analysis (at 6 months of treatment) and final analysis at the end of treatment, the following endpoints will be evaluated:

16.3.1 Primary Efficacy Endpoint:

- Compare the mean relative change in ALT & AST levels between the experimental arms and the control arm.
- Compare proportions of patients with normal ALT & AST at end of treatment between the experimental arms and the control arm. The cut-off values of ALT were 0-43 IU/L and of AST were 0-40 IU/L⁷.

16.3.2 Secondary Efficacy Endpoints:

- Comparing the mean change in Fib-4 score between the experimental arms and the control arm.
- Comparing the frequency and percentage of patients experiencing hepatic complications

⁶ Gpower 3.1

⁷ Uslusoy H, Nak S, Gülten M, Bıyıklı Z. Non-alcoholic steatohepatitis with normal aminotransferase values. World Journal of Gastroenterology. 2009;15(15):1863.

between the experimental arms and control arm.

16.3.3 Exploratory Endpoint:

- Compare the mean relative change in lipid profile levels between the experimental arms and the control arm.

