16.4 STATISTICAL ANALYSES

The statistical analysis of this study will consist of reporting of individual data listings, providing descriptive statistics for parameters of interest, and statistical testing of the primary and secondary variables.

The final statistical analyses will be performed when the patients on Heptex and placebo complete 9 months of treatment.

Detailed analysis methods will be provided in the statistical analysis plan.

16.4.1 Descriptive analysis:

- Percent (%) distribution for all categorical variables and mean with (SD) and median (Minimum: Maximum) for continuous variables according their distribution.

16.4.2 Primary analysis:

- The main objectives of this phase II study is to explore the anti-oxidant activity of Heptex as assessed by improvement in serum aspartate aminotransferase (AST) and alanine aminotransferase (ALT) levels by measuring:
- The mean relative change in ALT & AST levels between the experimental arms and the control arm from baseline till end of treatment using T-test (Mann-Whitney test in case of non-parametric data). This analysis will be a comparative analysis and will be done on eligible population of patients without protocol violation and who have at least one treatment dose and an evaluable primary endpoint (AST and ALT).
- Number of patients with normal ALT & AST at end of treatment between the experimental arms and the control arm. The cut-off values of ALT were 0-43 IU/L and of AST were 0-40 IU/L⁸ using chi square (Fischer test for non-parametric data). This analysis will be comparative analysis and will be conducted on the eligible population of patients without protocol deviation, who have at least one treatment dose and an evaluable primary endpoint (ALT and AST).

All tests will be performed on the 5% level of significance.

⁸ Uslusoy H, Nak S, Gülten M, Bıyıklı Z. Non-alcoholic steatohepatitis with normal aminotransferase values. World Journal of Gastroenterology. 2009;15(15):1863.

Procedure for accounting for missing, unused, and spurious data will be explained in the statistical analysis plan.

Any deviation(s) from the original statistical plan will be described in the final report).

16.4.3 Secondary analysis:

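### Six to eight comparisons are all primary, each tested at 5% with no lead comparison or order, so the final analysis carries about a 20–30% chance of some false-positive primary result and 9–16% of a false claim of benefit

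*Protocol*

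**What the plan says.** Section 16.3.1 lists two primary endpoints. The first is to "Compare the mean relative change in ALT & AST levels between the experimental arms and the control arm". The second is to "Compare proportions of patients with normal ALT & AST at end of treatment between the experimental arms and the control arm". Section 16.4.2 gives each its own test: a t-test or Mann–Whitney test for change, and chi-square or Fisher for normalisation. It then sets one level for everything: "All tests will be performed on the 5% level of significance". The synopsis repeats the endpoints, the tests and the level.

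There are two experimental arms. Under section 10.1, patients are "randomized in a 1:1:1 allocation ratio, into one of the three treatment groups, to receive either placebo or one of the two doses of Heptex".

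Section 16.1 sizes the trial from ALT only, with "a sample power of 80% and an effect size between placebo and lowest active dose of 0.63". Nothing there or elsewhere makes that comparison the deciding one. The protocol also does not say whether one significant primary result is enough or all are needed, or in what order they are read.

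**The concern.** When several comparisons carry the primary label and each may be significant at 5%, the 5% describes each test and not the trial's conclusion. With no effect of either dose, the chance that at least one primary result is significant is well above 5%. Because no comparison leads, any one of six to eight results could afterwards be presented as the positive primary outcome, including results for which the trial was not sized.

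This arises at the final analysis alone and would remain if the interim look were removed.

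**Working it through.** **1. Count the primary comparisons.**
- Relative change: 2 enzymes × 2 doses = 4.
- Normalisation: 2 enzymes × 2 doses = 4, or 1 both-normal outcome × 2 doses = 2.
- Total: 8 or 6.

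**2. Reproduce the plan's own figure.** Section 16.1 gives effect size 0.63, 80% power, a Mann–Whitney test and 43 per arm. Take the t-test size and multiply by π/3 for Mann–Whitney efficiency under normality.
- Two-sided 5%: 40.53 × π/3 = 42.4, so 43. Power at 43 is 80.5%.
- One-sided 5%: 31.85 × π/3 = 33.4, so 34.

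The stated 43 therefore matches one two-sided 5% test, although section 16.1 words it "with an alpha error of 5% using one-sided 95% CI of Mann–Whitney U test". That mismatch is a separate matter. What counts here is that 43 buys 80% power for one comparison.

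**3. Upper reference, as if the tests were independent.** 1 − 0.95^8 = 33.7%, and 1 − 0.95^6 = 26.5%. Both overstate the rate, because the tests are correlated.

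**4. Allow for correlation.** With 1:1:1 allocation and a shared placebo arm, the two dose contrasts have correlation (σ²/n) / (2σ²/n) = 0.5. The protocol gives no ALT–AST correlation, no correlation between change and normalisation, and no expected proportion normal, so these are assumptions:
- ALT–AST correlation 0.5 to 0.9.
- Multivariate-normal version: change–normalisation correlation 0.4 to 0.8.
- Patient-level version: 43 per arm, baseline medians of 70 (ALT) and 50 (AST), and the protocol's cut-offs of 43 and 40 IU/L.

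Results with no treatment effect, final analysis only, each test two-sided 5%:

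| Set of tests | Any false positive | False benefit |
|---|---|---|
| One test | 5% | 2.5% |
| ALT change, two doses | about 9% | – |
| Four change tests | 13–16% | – |
| Six tests, patient-level | 20–23% | 10–12% |
| Eight tests, patient-level | 24–28% | 12–14% |
| Eight tests, multivariate normal | 19–28% | 10–14% |

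Letting the proportion normal at end run from 10% to 50% gives roughly 20–30% for any false positive and about 9–16% for false benefit. On the six-test reading some settings fall a little lower, to about 17% and 8%.

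If each test were one-sided at 5%, as section 16.1 words it, the eight-test figure for false benefit is 17–26%, against 5% for one such test.

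**5. Would an all-must-win rule protect the error rate?** Yes. Requiring ALT change, AST change and both-normal all to succeed for a dose gives under 1% in the patient-level simulation. The protocol states no such rule.

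**The case against.** **The 5% sentence is not wrong in itself.** A fixed testing sequence also runs each test at the full 5%. A reader might infer that the sentence rules out multiplicity control, and it does not. A testing order could also sit in the SAP, which is not at hand, and section 16.4 defers detailed methods to it. This stands in part: the missing order alone would not be a finding. But the protocol itself puts all these comparisons in the primary set at 5% without saying how many must succeed. It defers detailed methods and missing-data handling, and nowhere the choice of primary comparison.

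**Eight is one reading.** Section 16.4.2 can be read as one both-normal outcome per patient. Since inclusion criterion 4 requires only one of the two enzymes to be elevated, that reading is at least plausible. This stands, so the count is six to eight. The conclusion is the same for both.

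**The larger percentage counts both directions.** A reader might take 20–30% as the chance of a false claim that Heptex works. It is not: about half of those results favour placebo. The figure for false benefit is 9–16%, and its comparator is 2.5%.

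**Phase II, with objectives worded as exploration.** How strictly to control the error rate here is partly judgement, and this limits the weight of the point. One might reply that significance stops the trial, but the only stopping-for-significance rule (sections 16.4.5 and 19) belongs to the interim analysis. At the final analysis the protocol ties no decision to a single p-value, so that argument is not used here. What remains is that formal tests labelled primary will be read at a nominal 5%.

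**Leading with ALT departs from the primary objective**, which names both enzymes. This is a fair cost. Keeping AST in the sequence reduces it.

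**Conclusion.** The point holds in a limited form. As written, six to eight comparisons are primary, each at 5%, with no lead comparison, order or all-must-win rule, while the sample size supports one. At the final analysis alone, the chance of at least one false-positive primary result is roughly 20–30% in either direction, or about 20–23% with six tests. The chance of a false claim of benefit is about 9–16%, against 2.5% for one two-sided test.

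These sizes rest on 43 evaluable per arm, an assumed ALT–AST correlation of 0.5–0.9 and an assumed 10–50% normal at end. The direction does not depend on the exact values. The documents do not support the 34% independence figure or a firm count of eight. It should be corrected, but it does not invalidate the design.

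**What to change.** In sections 16.3.1 and 16.4.2 and in the synopsis:

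1. Name one lead primary comparison that matches the sample-size basis: ALT change at week 36, lowest active dose against placebo, two-sided 5%.
2. Test the other dose on ALT change only if the first is significant, again at 5%.
3. Then test AST change and normalisation in a pre-stated order under the same rule, or label them supportive.
4. State whether normal ALT & AST means both enzymes normal in the same patient.

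This is an order of testing and implies nothing about which dose is preferable.

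The sequence holds the final-analysis error at 5% and leaves the 43 per arm for the first test unchanged. That power figure keeps the limits of section 16.1, which argues from an absolute fall in ALT of 20 U/L on placebo and double that on active, whereas the endpoint is relative change.

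Splitting alpha costs more:
- Over the two doses (0.05/2 = 0.025 each): 52 evaluable or 58 randomised per arm (58 × 3 = 174), or power of about 72% at 43.
- Over all eight (0.05/8 = 0.00625 each): 70 evaluable or 78 randomised per arm (78 × 3 = 234), or power of about 52% at 43.

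**Cost.** No added patients or visits. Later comparisons carry no formal claim if an earlier one fails, and AST ranks below ALT although the primary objective names both. The amendment should be made before unblinding. The interim look needs its own alpha and is a separate point.

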7.2 SECONDARY

- To explore the optimum dose that is safe in patients with apparent risk factors of NASH giving the most significant effect among two different doses of Heptex.
- To explore the hepatoprotective effect of Heptex as assessed by the change in Fibrosis score.
- To explore the hepatoprotective effect of Heptex as assessed by the occurrence of hepatic complications.

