8 STUDY DESIGN

8.1 DESCRIPTION OF THE STUDY DESIGN

This is a phase II, randomized, double blind placebo-controlled, three-arm, parallel-group, interventional clinical trial evaluating anti-oxidant activity of Heptex; a herbal medicinal product of Aerial Parts of *Phyllanthus niruri* (Dukung Anak) and Fruits of *Silybum marianum* (Milk Thistle).

Study duration: 12 weeks of recruitment and 36 weeks of treatment. This period will include 2 washout periods (at Week 13 & Week 25).

Sample Size: 47 subjects per arm, 141 in total.

Participants in trial will be patients between 18 and 65 years consenting to participate in this study, who have elevated liver enzymes^[34], controlled attenuation parameter (CAP)-confirmed hepatic steatosis, and Fib score of F1 and F2 assessed by the FibroScan liver stiffness measurement.

FibroScan will be done for all patients at screening visit and those with F1 and F2 will be considered for inclusion in the study. FibroScan will be repeated for all patients after 6 months and at the end of treatment duration and results will be compared.

Screening of patients will be continued for about 12 weeks. Eligible patients will be randomized in a 1:1:1 allocation ratio, into one of the three treatment groups, to receive either placebo or one of the two doses of Heptex. Randomization will be done using interactive response technology.

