8.4 DATA TO BE COLLECTED AT DIFFERENT STUDY INTERVALS

Screening visit:

During screening visit, data on informed consent process, inclusion and exclusion criteria, demographics, medical and surgical history, concomitant medications, physical examination, vital signs, FibroScan liver stiffness measurement (KPa), abdominal ultrasound, controlled attenuation parameter (CAP), lab tests (serum pregnancy test for females, PCR; HCV RNA, HAV IgM antibody test, HBsAg test, alpha fetoprotein, CBC, sodium, potassium, serum fibrinogen, albumin, bilirubin, prothrombin time, PTT, INR, ALT, AST, kidney function tests, lipid profile, and HbA1c) will be collected. Then Fib-4 score will be calculated.

Baseline (week 0):

At baseline visit, data on concomitant medications, physical examination and vital signs will be collected. Then occurrence of adverse events and serious adverse events

including hepatic complications will be collected. Data on the dispensed drug will be recorded.

Week 8 and week 12:

At week 8 and week 12, data on concomitant medications, physical examination, vital signs, controlled attenuation parameter (CAP), lab tests (serum pregnancy test for females, CBC, serum fibrinogen, albumin, bilirubin, prothrombin time, PTT, INR, ALT and AST) will be collected. Then Fib-4 score will be calculated and occurrence of adverse events and serious adverse events including hepatic complications will be collected. The drug accountability for the dispensed drug will be recorded.

Week 24:

At week 24, data on concomitant medications, physical examination, vital signs, FibroScan liver stiffness measurement (KPa), controlled attenuation parameter (CAP), lab tests (serum pregnancy test for females, CBC, sodium, potassium, serum fibrinogen, albumin, bilirubin, prothrombin time, PTT, INR, ALT, AST, kidney function tests, lipid profile and HbA1c) will be collected. Then Fib-4 score will be calculated and occurrence of adverse events and serious adverse events including hepatic complications will be collected. The drug accountability for the dispensed drug will be recorded.

Week 36:

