- The mean change in Fib-4 score between the experimental arms and the control arm from baseline till end of treatment using T-test (Mann-Whitney test in case of non-parametric data). This analysis will be a comparative analysis and will be done on eligible population of patients without protocol violation and who have at least one treatment dose and an evaluable primary endpoint (AST and ALT).
- Number of patients experiencing hepatic complications between the experimental arms and control arm at the end of the treatment using chi-square (Fischer for non-parametric data). This analysis will be a comparative analysis and will be done on eligible population of patients without protocol violation and who have at least one treatment dose and an evaluable primary endpoint (AST and ALT).

16.4.4 Exploratory analysis:

- The mean relative change in lipid profile levels between the experimental arms and the control arm from baseline till end of treatment using T-test (Mann-Whitney test in case of non-parametric data). This analysis will be a comparative analysis and will be done on eligible population of patients without protocol violation and who have at least one treatment dose and an evaluable primary endpoint (AST and ALT).

16.4.5 Interim analysis:

- Interim analysis will be performed when all patients complete 6 months of treatment. If a statistically significant difference is observed between placebo and active arm(s), the study will be terminated for the benefit of patients who were randomly assigned to placebo arm and to rapidly disseminate evidence supporting a treatment benefit to the broader community⁹.

⁹Zannad F, et al. Development of Therapeutics for Heart Failure. When to Stop a Clinical Trial Early for Benefit: Lessons Learned and Future Approaches. *Circulation: Heart Failure*. 2012; 5: 294-302. doi: 10.1161/CIRCHEARTFAILURE.111.965707

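### The Fib-4 secondary endpoint is built from the AST and ALT of the primary endpoint, so an enzyme effect alone can shift it in either direction and be taken for a fibrosis effect

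*Protocol*

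**What the plan says.** The first primary endpoint in protocol 16.3.1 is "Compare the mean relative change in ALT & AST levels between the experimental arms and the control arm"; the second is the proportion with normal values of the same two enzymes.

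A secondary objective in 7.2 is "To explore the hepatoprotective effect of Heptex as assessed by the change in Fibrosis score". The endpoint that answers it, in 16.3.2, is "Comparing the mean change in Fib-4 score between the experimental arms and the control arm". Section 16.4.3 sets its analysis as "The mean change in Fib-4 score between the experimental arms and the control arm from baseline till end of treatment using T-test", or a Mann-Whitney test for non-parametric data, and 16.4.2 adds "All tests will be performed on the 5% level of significance" without saying one- or two-sided. Section 16.3 has these endpoints evaluated at the 6-month interim as well as at the end.

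For weeks 8 and 12, section 8.4 describes the laboratory work and the score together: "CBC, serum fibrinogen, albumin, bilirubin, prothrombin time, PTT, INR, ALT and AST) will be collected. Then Fib-4 score will be calculated". The descriptions for weeks 24 and 36 follow the same order. No formula is printed.

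A fibrosis measure that is not computed from the enzymes is also collected. FibroScan stiffness is scheduled at screening, week 24 and week 36, and 8.1 says "FibroScan will be repeated for all patients after 6 months and at the end of treatment duration and results will be compared". It is not a listed endpoint and no test is assigned to it.

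**The concern.** Over 36 weeks a patient's age barely changes, so Fib-4 can move only through AST, ALT and platelets. The treatment is expected to lower two of those three, and the trial is sized on one of them. A difference in Fib-4 between arms may therefore restate the primary result with different weights.

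The weights make the direction unreliable. AST enters in full and ALT as an inverse square root. Lowering both in proportion makes the score look better; lowering mainly ALT makes it look worse. Inclusion criterion 4 accepts elevation of either enzyme, so the two need not move together.

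What is at stake is the answer to a secondary objective, at the interim and the final analysis. Nothing in 7.2, 16.3.2 or 16.4.3 acknowledges the overlap or separates an enzyme effect from a fibrosis effect. The primary test is not affected.

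**Working it through.** **Inputs from the protocol (16.1).** ALT falls by 20 U/L on placebo and by twice that, 40 U/L, on active; standardised effect 0.63; 80% power; 43 evaluable per arm.

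**Reproducing 43.** A Mann-Whitney sample size (noncentral t, relative efficiency 3/pi) with effect 0.63, 80% power and two-sided 5% gives 43. The one-sided version, as 16.1 words it, gives 34. I use 43 per arm and a two-sided 5% test below.

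**Assumptions not in the protocol.** Standard Fib-4 formula; screening ALT of 60 to 120 U/L; no treatment effect on platelets or fibrosis.

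**Direction, from the formula alone.** With age and platelets fixed, the Fib-4 ratio to screening is (AST ratio) / sqrt(ALT ratio). Let D be the log ALT ratio of active to placebo, and let the log AST change be k times the log ALT change. Then

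log(Fib-4 active / Fib-4 placebo) = kD - D/2 = (k - 1/2) D.

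Since D is negative, Fib-4 falls when k exceeds 1/2, rises when k is below 1/2, and does not move at k = 1/2.

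| Screening ALT | ALT ratio placebo / active | D | Fib-4 active/placebo, proportional AST (k = 1) | Flat AST (k = 0) |
|---|---|---|---|---|
| 60 | 0.667 / 0.333 | -0.693 | 0.707 | 1.414 |
| 80 | 0.750 / 0.500 | -0.405 | 0.816 | 1.225 |
| 100 | 0.800 / 0.600 | -0.288 | 0.866 | 1.155 |
| 120 | 0.833 / 0.667 | -0.223 | 0.894 | 1.118 |

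For example, at ALT 80 with proportional AST: 0.500/sqrt(0.500) = 0.707 on active, 0.750/sqrt(0.750) = 0.866 on placebo, and 0.707/0.866 = 0.816.

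Near-cancellation covers a band, not a single point. If AST is 20% and ALT 40% lower than on placebo, the ratio is 0.8/sqrt(0.6) = 1.033. At 30% and 50% it is 0.7/sqrt(0.5) = 0.990.

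**Chance of a significant result without a fibrosis effect.** I simulated one active arm against placebo, 43 per arm, with a two-sided 5% t-test on the raw change in Fib-4 and 6000 trials per setting. Assumed: median screening Fib-4 1.3 with log-SD 0.4; correlation of AST and ALT log changes 0.7; platelet log-SD 0.12; AST log-SD equal to 0.875 (0.35/0.40) times that of ALT. The ALT log-SD is |D|/0.63, so that the ALT effect matches the protocol's: 0.693/0.63 = 1.10, 0.405/0.63 = 0.64, 0.288/0.63 = 0.46 and 0.223/0.63 = 0.35 at ALT 60, 80, 100 and 120.

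| k (log AST change / log ALT change) | ALT 60 | ALT 80 | ALT 100 | ALT 120 | Direction |
|---|---|---|---|---|---|
| 1 (proportional) | 46% | 48% | 47% | 44% | Fib-4 lower on active |
| 0.75 | 15% | 16% | 15% | 15% | almost all lower |
| 0.5 | 5% | 5% | 5% | 5% | both, evenly |
| 0 (AST flat) | 44% | 48% | 46% | 44% | Fib-4 higher on active |

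**Sensitivity to the variance.** Fixing the ALT log-SD at 0.40 and the AST log-SD at 0.35 gives, with proportional AST, 82%, 54% and 38% at ALT 80, 100 and 120. But 0.405/0.40 = 1.01 is then the standardised ALT effect at ALT 80, well above the 0.63 on which the trial is sized. The calibrated rates are the ones to use.

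**The case against.** The protocol says nothing false about Fib-4. That the index contains AST and ALT is a property of the index, the trial is phase II, and the objective is only to explore. The protocol never says that a Fib-4 difference will be called anti-fibrotic. That is right, and a reader who infers that the plan commits the sponsor to such a claim goes too far. What stands is that 7.2 ties hepatoprotection to a fibrosis score and that Fib-4 is the only such score given a test. The misreading is left open, not prescribed.

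A reader might also infer that a spurious result is close to certain, at about 80%. That needs a low ALT variance which conflicts with the protocol's effect size; calibrated, the rate stays below one half even at the extremes. Nothing in the protocol shows that either extreme is likely, and between them the rate drops to 15% and to 5%.

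Nor is it true that the trial lacks any enzyme-free reading of fibrosis. FibroScan is repeated and is to be compared. It is a partial safeguard only, because it is neither an endpoint nor assigned a test.

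Finally, with AST and ALT frozen at screening, Fib-4 varies only with age and platelets, and may move little in F1 to F2 patients over 36 weeks. Making that score the sole condition for a fibrosis claim could suppress a true effect. This objection stands and shapes the fix.

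**Conclusion.** The point holds in a limited form. Under the standard formula, the raw Fib-4 change cannot separate an enzyme effect from a fibrosis effect, and its sign depends on which enzyme falls more. The direction needs only the formula and unchanged platelets.

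The size is less certain. The chance of a significant Fib-4 difference with no fibrosis effect is roughly 44% to 48% if AST either follows ALT fully or does not move, about 15% at three quarters, and the nominal 5% at one half. These figures depend on assumed SDs, correlation and baseline values, on reading the 0.63 as applying to the log ALT change, and on a two-sided t-test for one comparison. The Mann-Whitney alternative was not simulated. The consequence is confined to how a secondary objective is answered.

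**What to change.** - In 16.4.3, print the Fib-4 formula and keep the planned comparison.
- In 16.4.3, add as a sensitivity analysis the same comparison on Fib-4 recomputed with AST and ALT held at their screening values.
- Apply the same between-arm test to the change in FibroScan stiffness from screening, using the week 24 and week 36 measurements.
- In 7.2, name the measure meant by the fibrosis score, since 8.1 uses a similar term for the FibroScan stage.
- In 7.2 and 16.3.2, state that a Fib-4 difference alone will not be reported as a fibrosis effect separate from the AST/ALT change, and that it will be interpreted beside FibroScan and the sensitivity analysis. Do not make the enzyme-held-constant score the sole gate.

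The cost is one derived variable, two further comparisons and some wording, all from data already scheduled. The downside is that a fibrosis claim becomes harder to make, and the enzyme-held-constant score is insensitive over 36 weeks, so no difference in it would not show that fibrosis is unchanged.

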9.2 INCLUSION CRITERIA

- 1) Male or female aged between 18 and 65 years.
- 2) Both male and female patients who have childbearing potential must agree to practice an acceptable method of birth control during the study and for at least 6 months after the cessation of treatment; such contraceptive methods must include at least one barrier method.
- 3) Controlled Attenuated Parameter (CAP)-confirmed hepatic steatosis.
- 4) Patients with elevated Liver enzymes (ALT and/or AST) ^[34].
- 5) Liver fibrosis stage F1-F2 as diagnosed by the FibroScan liver stiffness measurement of 5-10 kPa.
- 6) liver condition according the following criteria;
 - Serum albumin > 3 g/dl
 - INR < 2
 - No ascites on ultrasound
 - No documented or suspected hepatic encephalopathy
- 7) Willing to stop any other liver support and hepatoprotective medications throughout study duration.
- 8) Able and willing to provide written informed consent.
- 9) Able and willing to complete all study visits and procedures, including compliance with the requirements and restrictions listed in the consent form.

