11 CONCOMITANT MEDICATIONS

Throughout the study, investigators may prescribe any concomitant medications or treatments deemed necessary to provide adequate supportive care except other liver support, hepatoprotective medications and any medications prohibited as per the eligibility criteria. If these are required, the participant will be withdrawn. Any medication, other than the study medication taken during the study will be recorded in the CRF.

Any medication or vaccine (including over-the-counter or prescription medicines, vitamins and/or herbal supplements) that the subject is receiving during participation in the study must be recorded in the electronic case report form. The investigator should review all concomitant medications for any potential interactions. During the Post-Treatment Period, all medications will be collected.

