16.2 ANALYSIS POPULATIONS

The obtained clinical data will be analyzed on an intention-to-treat basis. Primary analysis will be done by intention-to-treat including all eligible enrolled patients with at least one treatment dose and post first dose assessment (ALT & AST) attending any post treatment visit and efficacy variables will be analyzed using the last-observation-carried-forward convention (LOCF).

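### The rule for who is counted in the hepatic-complications comparison can lose the patients who have the event, and a low count should not be read as hepatoprotection

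*Protocol*

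**What the plan says.** Protocol section 7.2 lists as a secondary objective "To explore the hepatoprotective effect of Heptex as assessed by the occurrence of hepatic complications". Section 16.3.2 places the measure among the secondary efficacy endpoints. Section 16.4.3 fixes the comparison as the "Number of patients experiencing hepatic complications between the experimental arms and control arm at the end of the treatment using chi-square", with Fisher as the alternative, and restricts it to the "eligible population of patients without protocol violation and who have at least one treatment dose and an evaluable primary endpoint (AST and ALT"). The synopsis repeats this.

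Section 16.2 describes a different population. It declares an intention-to-treat basis and asks for at least one dose and a "post first dose assessment (ALT & AST) attending any post treatment visit and efficacy variables will be analyzed using the last-observation-carried-forward convention (LOCF"). The two sections are not reconciled.

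Entry under section 9.2 requires "Liver fibrosis stage F1-F2 as diagnosed by the FibroScan liver stiffness measurement of 5-10 kPa", albumin above 3 g/dl, INR below 2, "No ascites on ultrasound" and "No documented or suspected hepatic encephalopathy". Section 9.3 excludes liver cancer. Treatment lasts 36 weeks.

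The assessment schedule (section 2) places ALT/AST at screening and weeks 8, 12, 24 and 36, and records hepatic complications at every visit from week 0. It shows no early-termination visit. On liver-support, hepatoprotective and other prohibited medication, section 11 says "If these are required, the participant will be withdrawn". Section 18 lists disease progression among the reasons for discontinuation.

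**The concern.** A patient either has a hepatic complication or does not, and no later enzyme value is needed to know which. Requiring an evaluable ALT/AST and a clean protocol record selects patients on post-randomisation data, and that selection can be related to the event itself. If event patients are lost, the arm with more events loses more of them and the arms look more alike than they are. If the loss differs between arms, the bias can go either way.

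The second issue is interpretation. The endpoint is offered as a measure of hepatoprotection in early, compensated disease over 36 weeks, in a trial sized on ALT. If few or no events occur in any arm, the result could be reported as no difference, or as protection maintained, when it supports neither.

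**Working it through.** **1. Who is counted.** The two population rules, applied to a treated patient who has a complication:

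| Patient leaves | Section 16.2 | Section 16.4.3 |
|---|---|---|
| Before the week 8 sample | No scheduled post-dose ALT/AST: not counted | No evaluable ALT/AST: not counted |
| After week 8, before week 36 | Has a post-dose value: counted | Counted only if *evaluable* does not mean an end-of-treatment value and the withdrawal is not classed as a violation |
| Completes, with a protocol violation | Counted | Not counted |

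The first row is a loss under both rules. The other two rows are where the sections conflict or leave the answer open.

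**2. The plan's own figure.** Section 16.1 gives 43 evaluable and 47 enrolled per arm, from an ALT effect size of 0.63 and 80% power. With a Mann-Whitney efficiency of 3/π and a two-sided 5% test, 43 per arm gives 80.5% power, so the figure reproduces on that basis. (The one-sided test named in the text would give 34; that is a separate matter.) The protocol states no rate, effect or power for hepatic complications, so there is no figure to reproduce for this endpoint.

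**3. Events needed for significance.** Assumptions: two-sided 5% level, 47 per arm, no events on active treatment.

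- One active arm v placebo, Fisher, p = 2 × C(47,k)/C(94,k): k = 5 gives 0.056; k = 6 gives 0.026. At least 6/47 = 12.8% is needed.
- Same comparison, uncorrected chi-square: 4 v 0 gives p = 0.041.
- Both active arms pooled (94) v placebo (47), Fisher, p = C(47,k)/C(141,k): k = 3 gives 0.035, so 3 events are enough.

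Section 16.4.3 does not settle whether the arms are compared singly or pooled, so both are shown.

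**4. Power if the drug prevents every event.** This is P(X ≥ k) for X ~ Binomial(47, p), where p is an assumed placebo rate over 36 weeks.

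| Assumed p | Expected placebo events (47p) | One arm, k = 6 | Pooled, k = 3 |
|---|---|---|---|
| 2% | 0.94 | 0.03% | 7% |
| 5% | 2.35 | 2.9% | 42% |
| 10% | 4.7 | 33% | 86% |
| 20% | 9.4 | 93% | above 86% |

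Reaching 80% power needs a placebo rate of about 16.5% (one arm) or 9% (pooled). If the drug only halves the rate, one-arm power by Fisher is 1.0% at 5%, 5.6% at 10% and 18% at 20%.

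**5. Cost of losing event patients.** Take p = 10%, one arm, total prevention. If a share d of event patients is not counted, the observed rate is 0.10(1 − d)/(1 − 0.10d). For d = 0.5 this is 0.05/0.95 = 5.3%, and power falls from 33% to 3.6%. For d = 0.25 it is 7.7%, and power is 15%. These figures keep 47 patients analysed, for simplicity. The documents do not say what d would be.

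**6. What zero events would show.** The exact 95% upper limit for 0/47 is 1 − 0.025^(1/47) = 7.5%. An arm without events is compatible with a true rate up to that value.

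**The case against.** The strongest reply is that nothing in the protocol removes a patient from analysis for leaving because of a hepatic event. Section 18 lists significant protocol deviation and disease progression as separate reasons, so progression is not itself a violation. Under 16.2 anyone with a week 8 value stays in. This stands: the only clear-cut loss of leavers is before week 8, and the later losses depend on readings the text leaves open.

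A reader might infer that a patient with a complication will need liver-support medication and so be withdrawn under section 11. The text is conditional and does not say so. It also allows other supportive treatment, and the protocol does not define hepatic complications.

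A reader might also infer that the rule hides a safety signal. It does not. Section 16.4.3 governs an efficacy comparison. Complications are collected with adverse events at every visit from week 0, all adverse events are recorded regardless of relationship, serious events are notified within 24 hours, and individual data listings are planned.

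Finally, the objective is exploratory, the trial is phase II, and a secondary endpoint need not be powered. This stands too. It answers a complaint about low power alone, but it does not justify the population rule or a protective reading of a low count.

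**Conclusion.** The point holds as a defect in the analysis population, with a caution on interpretation. Section 16.4.3 can lose event patients. It certainly does so for treated patients who leave before week 8 without a post-dose sample, and possibly for later leavers. It also conflicts with 16.2 on who is counted. How many events this would affect cannot be derived from the protocol.

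The stronger claim that the endpoint cannot test hepatoprotection is not supported, because it needs an event rate the documents do not give. At assumed placebo rates of 2% to 5%, a one-arm Fisher comparison has power below 3% even if every event is prevented. Pooling raises this to between 7% and 42%, and at 20% the one-arm comparison reaches 93%. What does follow is that entry criteria selecting early, compensated disease, together with 36 weeks of follow-up, make low counts plausible, and low counts would be uninformative about protection. Whether the endpoint is labelled efficacy or safety is a matter of preference.

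**What to change.** 1. In section 16.4.3 and the synopsis, count hepatic complications in every randomised patient who took at least one dose, from first dose to last contact. Drop the requirements for an evaluable ALT/AST and for no protocol violation on this endpoint.
2. Reconcile section 16.2 with this, so that one population is named for the endpoint.
3. Report counts per arm with exact confidence intervals, and say whether the active arms are compared with placebo singly or pooled.
4. State in advance that few or no events will not be read as evidence of hepatoprotection.

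The cost is a wording change in the protocol and synopsis. No new data are needed, because complications are already recorded at every visit from week 0. The sponsor gives up only the option of presenting a low count as support for the objective.
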